### ABSTRACT

Rationale: Men who have sex with men (MSM) continue to be disproportionately affected by HIV. The majority of HIV infections among MSM occur through exposure to the rectal mucosa during receptive anal intercourse (RAI). To aid in prevention, a new HIV prevention intervention, called pre-exposure prophylaxis (PrEP), recommends that MSM at risk of HIV infection take a daily anti-HIV medication called Truvada® (tenofovir/emtricitabine) which is shown to be highly effective. However, current tenofovir- based regimens have shown to cause different side effects while taken. To reduce these side effects, new formulations of anti-HIV agents are being developed, but the ability of these new agents to penetrate mucosal tissues and prevent HIV infection at sites of virus exposure is unclear.

**Design:** To address the efficacy of the new formulated anti-HIV agents and their ability to penetrate the mucosal tissues in MSM, investigators at Emory University will collaborate with the Centers for Disease Control and Prevention (CDC) to conduct a randomized clinical trial of 90 MSM. Men will be randomized into a 2-arm study (fortyfive men assigned to each arm) as follows: (Arm 1) daily oral Truvanda® or (Arm 2) daily oral Genvova®. Each study arm includes 3 phases: (1) pre-drug, (2) short-course, and (3) steady state. For phase I, there will be 5 men assigned to both arm 1 and arm 2. Phases II and III will each have 20 men assigned to both arms. The study will entail 2 study visits for phase I, 3 study visits for phase II, and 4 study visits for phase III at the Emory University Hope Clinic. During phase I: visit 1, all men will be screened for eligibility and undergo written informed consent, physical examination, rapid HIV testing, phlebotomy for screening laboratories, and randomization. During study visit 2 (time 1-6 weeks after study visit 1), participant returns and a urethral swab, 2 pre- wet penile swabs, and a urine sample will be collected. Participant will then undergo a rectal biopsy via rigid sigmoidoscopy for establishment of baseline values. During phase II: study visit 1, men will be screened for eligibility and undergo written informed consent, physical examination, rapid HIV testing, phlebotomy (will collect 4 tablespoons) for screening laboratories, and randomization. During study visit 2 (time 1-6 weeks after study visit 1), men will be dispensed and instructed to take either one dose of Truvada® or Genvoya®. After 4 to 6 hours after dosing, a urethral swab, 2 pre- wet penile swabs, 4 tablespoons of blood, and a urine sample will be collected. During study visit 3 (time 24 hours after drug dosing), men will return after 24 hours of study product use for repeat phlebotomy, urethral and penile swabs, collection of urine and rectal secretions, and rectal biopsy via rigid sigmoidoscopy. For phase III: visit 1,

men will be screened for eligibility and will undergo the informed consent process. Once informed consent is signed, a physical examination will be performed, rapid HIV testing, phlebotomy for screening labs, and randomization will occur. During study visit 2 (time 1-6 weeks after study visit 1), men will be dispensed and instructed to take either Truvada® or Genvoya® for 10 days. After 3 to 5 consecutive days of dosing, participants will return for visit 3 where a urethral and penile swabs specimen, blood work, and a urine specimens will be obtained. During study visit 4 (time 10 days of consecutive drug dosing), men will return for repeat phlebotomy, urethral and penile swabs, collection of urine and rectal secretions, and rectal biopsy. After collection, biologic specimens will be immediately transported by courier to CDC (laboratory of [name]) for processing. Specimens will be processed immediately for ex vivo laboratory assays that will include Truvada® and/or Genvoya® drug concentrations, inflammatory cytokine levels, HIV target cell measurement and characterization by flow cytometry, and in vitro HIV infection assays. Comparison of assay results between the 2 study arms will help in determining the ability of the new formulated anti-HIV drug to penetrate different body compartments at the site of possible HIV exposure.

Participants may participate in more than one phase; however, at least 8 weeks must lapse after completion of 1 study phase before entry into another. Men who participate in more than one phase will not be consented again and do not have to repeat the screening visit (visit 1) when starting another phase; they will begin the new phase at visit 2.

Duration: The duration of this study is 3 years. Participants will be considered 'on-study' for no more than 12 weeks.

Sample size: For this protocol we will recruit 90 HIV-negative MSM or transgender women who are not taking hormone therapy who meet eligibility criteria outlined in the protocol.

Population: The population to be studied in this protocol is HIV negative MSM and transgender women who are not taking hormone therapy, who meet eligibility criteria, and are willing to perform study procedures. Participants will be recruited from existing databases at Hope Clinic and the Rollins School of Public Health who have agreed to be contacted for future studies, from community recruitment events conducted by the Hope Clinic, and from internet and paper advertisements currently used routinely by the Hope Clinic for study recruitment.

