For this protocol, we will recruit HIV-negative MSM and TGW who are not on hormone therapy aged 18-49 and who are willing to adhere to study procedures. There will be 3 phases, with 2 study visits for phase I, 3 study visits for phase II, and 4 study visits for phase III that will be conducted over a maximum period of 12 weeks. Participants are allowed to participate in more than one phase if a recovery or washout period occurs 8 weeks in between each phase. The first visit for all phases (phase I, phase II, and phase III) will be a screening visit where eligibility is determined, written informed consent is obtained, screening tests are performed, and men will be randomized to one of two study groups: 1. Use of oral Truvada®; or 2. Use of oral Genvoya®. During the second study visit (visit 2), men in phase I will not receive product, but will come in for blood work, urine sample, 2 pre-wet penile swabs, urethral swab, rectal swab, and rectal biopsy sampling. Participants who are in phase II will receive a single dose of the study product during visit 2, 1-6 weeks after the screening visit. MSM will return 4 to 6 hours after taking the drug for a urine sample. We will then collect 4 tablespoons of blood from the participants arm, in addition to, 2 pre-wet penile swabs, and a urethral swab. The third study visit will occur 24 hours from dosing time for MSM in phase II. Men will undergo a blood draw, urine sample, penile, urethral, and rectal swab, and rigid sigmoidoscopy for collection of rectal secretions and biopsies. Participants in phase III at study visit 2 will receive a 10-day supply of the study drug and will be instructed to take it for 10 consecutive days. For visit 3 in phase III, participants will return for a blood draw, urine collection, 2 pre-wet penile swabs, and a urethral swab to examine drug levels after 3-5 days of taking study drug. They will then return 10 days from dosage for visit 4, where blood, urine, penile, urethral, and rectal swabs will be collected, and rectal biopsy sampling will occur. All specimens will be transported directly to the laboratory of [name] at CDC where multiple immune assays are planned to determine the ability of these agents to penetrate mucosal tissues and potentially prevent HIV infection during RAI exposure.

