# STUDY POPULATION

A total of 90 HIV-negative MSM aged 18-49 will be recruited from existing Emory University study databases of MSM who have agreed to future contact about research opportunities. We will also recruit men from community engagements events conducted by Hope Clinic recruiters, from print and on-line advertisements, and from social media advertisements. Research recruiters at the Hope Clinic and the Rollins School of Public Health are experienced in recruiting this population for research studies, including those with rectal biopsies, and do not anticipate problems. [name] is has conducted 2 similar studies before and does not anticipate any problems with recruiting the target population. Based on our previous studies, we expect approximately 20% of men will not complete all study visits, therefore the sample size of 90 men will likely result in study completion for 72 men.

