# EXCLUSION CRITERIA

- History of inflammatory bowel disease or other inflammatory, infiltrative, infectious or vascular condition involving the lower gastrointestinal tract that, in the judgment of the investigators, may be worsened by study procedures or may significantly distort the anatomy of the distal large bowel
- 2) Significant laboratory abnormalities at baseline visit, including but not limited to:
  - a) Hgb  $\leq$  10 g/dL
  - b) PTT > 1.5x ULN or INR > 1.5x ULN
  - c) Platelet count <100,000
  - d) Creatinine clearance <60

- Any known medical condition that, in the judgment of the investigators, increases the risk of local or systemic complications of endoscopic procedures or pelvic examination, including but not limited to:
  - a) Uncontrolled or severe cardiac arrhythmia
  - b) Recent major abdominal, cardiothoracic, or neurological surgery
  - c) History of uncontrolled bleeding diathesis
  - d) History of colonic, rectal, or vaginal perforation, fistula, or malignancy
  - e) History or evidence on clinical examination of ulcerative, suppurative, or proliferative lesions of the anorectal or vaginal mucosa, or untreated sexually transmitted disease with mucosal involvement
- 4) Continued need for, or use during the 14 days prior to enrollment, of the following medications:
  - a) Aspirin or more than 4 doses of NSAIDs
  - b) Warfarin, heparin (low-molecular weight or unfractionated), platelet aggregation inhibitors, or fibrinolytic agents
  - c) Any form of rectally administered agent besides products lubricants or douching used for sexual intercourse
- 5) Continued need for, or use during the 90 days prior to enrollment, of the following medications:
  - a) Systemic immunomodulatory agents
  - b) Supraphysiologic doses of steroids
  - c) Experimental medications, vaccines, or biologicals
- 6) Intent to use HIV antiretroviral pre-exposure prophylaxis (PrEP) during the study, outside of the study procedures
- 7) Symptoms of an untreated rectal sexually transmitted infection (e.g. rectal pain, discharge, bleeding, etc.)
- 8) Current use of hormonal therapy
- 9) Any other clinical condition or prior therapy that, in the opinion of the investigator, would make the patient unsuitable for the study or unable to comply with the study requirements.

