# Phase II

40 participants (20 in each study arm) will be enrolled in study phase 2.

Study visit 2 will occur 1-6 weeks after the screening visit. During visit 2, the study group assignment will be reviewed and participants will be provided with a single dose of Truvada® or Genvoya®. Drug will be dispensed through the Emory Investigational Drug Service. Depending on the study arm they were assigned to, MSM will be dispensed 1 day of Truvada® or Genvoya® and instructed on dosing for that day. Four to six hours after the drug is taken, a urine sample, 4 tablespoons of blood will be drawn from the participants arm, as well as, penile and urethral swabs will be collected from participants. These sample will be used at CDC to develop an assay to detect Truvada® and Genvoya® in the body. All specimens will be coded with a unique numeric identifier such that the CDC laboratories that receive the specimens will be unable to link them back to the study participants. Participants will be requested to abstain from receptive anal intercourse 3 days prior to study visit 2 and while taking study product.

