# Contingency visit:

Attempts to ensure adherence to the study visits will be made with telephone and/or email reminders to the participant. However, if for example, screening laboratory results are lost or are inconclusive or if a participant has been unable to adhere to study protocol, he may be rescheduled for a future date where the above visit procedures will be performed. These additional visits will be scheduled within the above visit windows.

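### The protocol gives two times for randomisation; if the screening-visit text is followed, men are allocated to a named product before their eligibility is settled

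*Protocol*

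**What the plan says.** The Protocol's Abstract (Design) places randomisation at visit 1 in all three phases, alongside the screening blood draw:

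- Phase I: "rapid HIV testing, phlebotomy for screening laboratories, and randomization".
- Phase II: "phlebotomy (will collect 4 tablespoons) for screening laboratories, and randomization".
- Phase III: "rapid HIV testing, phlebotomy for screening labs, and randomization will occur".

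The Lay Summary says of the first visit, for every phase, that "screening tests are performed, and men will be randomized to one of two study groups".

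The Procedures section reads differently. Its Visit 1 text covers consent, history, examination, rapid HIV test and blood draw, but not randomisation. The sentence randomising participants to the two arms stands under the heading Visit 2. Further down under that heading, however, the Phase II text says that "the study group assignment will be reviewed and participants will be provided with a single dose", and Phase III has parallel wording. An assignment that is reviewed at visit 2 already exists by then.

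Visit 2 falls 1-6 weeks after screening. It is when product is first given in Phases II and III; Phase I gives no drug.

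**The concern.** The blood drawn at visit 1 decides the haemoglobin, coagulation, platelet and creatinine-clearance exclusions. The list of laboratory exclusions is open-ended, and criterion 9 excludes anyone with a condition that, "in the opinion of the investigator, would make the patient unsuitable for the study". If allocation comes first, the investigator may rule on borderline results and on criterion 9 with the arm known, and the participant may decide whether to return for visit 2 knowing his product.

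The text offers a concrete route. The section on Genvoya risks says that men known to have hepatitis B should not take part. The Truvada risk section does not mention hepatitis B and the exclusion list does not name it. A discretionary ruling could therefore differ by arm. Those passages need reconciling in their own right.

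What is at stake is the between-arm comparison, which is the Goal in the Project Description and the closing aim of the Design text. Post-dose drug levels and biopsies exist only for men who are dosed. If reaching the first dose depends on the arm, the compared groups are no longer those that randomisation created. Neither document says how men allocated but never dosed are to be handled.

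**Working it through.** **1. Timing, text against text.**

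| Place in Protocol | When randomised |
|---|---|
| Abstract, Phases I, II and III | Visit 1 |
| Lay Summary, all phases | Visit 1 |
| Procedures, Visit 1 | Not listed |
| Procedures, Visit 2, opening sentence | Visit 2 |
| Procedures, Visit 2, Phases II and III | Already assigned; reviewed at visit 2 |

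The two accounts cannot both hold. The Procedures section also disagrees with itself under its own Visit 2 heading.

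**2. Are laboratory results in hand at visit 1?** The blood is drawn at that visit. The Contingency visit section gives, as an example of a reason to reschedule, that "screening laboratory results are lost or are inconclusive", so results come back after the draw. The rapid HIV result is the exception: it is available on the day. No passage requires laboratory results before randomisation.

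**3. The plan's own figure.** Study Population states that "we expect approximately 20% of men will not complete all study visits" and gives 72 completers.
- 90 × (1 − 0.20) = 72, which reproduces it.
- Arms: 2 × 5 + 2 × 20 + 2 × 20 = 90.
- Per arm: 20 × 0.80 = 16 in Phases II and III; 5 × 0.80 = 4 in Phase I.

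The loss is not split by arm, nor into before and after dosing. Assuming anything from none to all of it is pre-dose, 0 to 4 of 20 men per arm would leave between allocation and treatment.

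**4. Illustration only.** If the lowest fraction l of a standard normal outcome is lost from an arm, its mean rises by φ(z_l)/(1 − l) SD. For l = 0.20 this is 0.280/0.80 = 0.35 SD. The standard error of an arm difference is √(1/n₁ + 1/n₂) SD.

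Milder case (assumed): 4 of 20 leave one arm and none the other, selected on a factor correlated r = 0.3 to 0.5 with the outcome.
- Shift: 0.35 × 0.3 = 0.105 SD to 0.35 × 0.5 = 0.175 SD.
- Standard error: √(1/20 + 1/16) = 0.335 SD.
- Ratio: 0.31 to 0.52 of a standard error.
- Overall loss here is 4/40 = 10%, half the plan's 20%.

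Harsher case (assumed): average loss held at 20%, all of it pre-dose, and selection acting on the outcome itself from the same tail in both arms.

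| Loss by arm | Men left | Spurious difference (SD) | Standard error (SD) |
|---|---|---|---|
| 20% / 20% | 16 v 16 | 0 | 0.354 |
| 15% / 25% | 17 v 15 | 0.15 | 0.354 |
| 10% / 30% | 18 v 14 | 0.30 | 0.356 |
| 5% / 35% | 19 v 13 | 0.46 | 0.360 |

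Equal 20% loss from opposite tails would give 0.35 + 0.35 = 0.70 SD.

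**5. Would it show in the counts?** With independent 20% loss in each arm of 20, completer counts differ by 4 or more with probability 0.16 by chance alone. Unequal counts would not by themselves prove the bias, and the opposite-tail case shows that equal counts would not exclude it.

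**The case against.** The strongest reply is that the operative text already randomises at visit 2. The Procedures section is the detailed one, it puts randomisation under Visit 2, and its Visit 1 list omits it. If that governs, most of the concern falls away. This stands as far as it goes, and it is why visit 1 randomisation cannot be called settled. It does not remove the problem: the Phase II and III text in that same section presupposes an earlier assignment, and nothing under Visit 2 says eligibility must be final first.

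It can also be said that the Lay Summary has eligibility determined at visit 1. That can be true of history, examination and the rapid HIV test, but not of results from blood drawn at that visit.

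Several stronger readings are tempting but unsupported:

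- *That the trial is open-label with early disclosure.* The products are named and no masking is described, so this is a fair inference. But the term never appears, and no passage says when anyone learns the arm.
- *That lost screening results are expected.* The Contingency visit section offers them only as an example.
- *That men who fail laboratory screening use up places in the 20 per arm.* No passage says so; the counts refer to men who are eligible or enrolled in a phase.
- *That later randomisation would improve precision.* Any gain would come from replacing lost men, which is a separate rule.
- *That participants are told things that favour one product.* The protocol's risk sections differ between products, but the consent text is not available. Consent precedes randomisation on either reading, so men have agreed to either product.

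The reach is also limited. The SAP's only test compares baseline with follow-up within person, and no between-arm test is specified. Men re-entering for another phase skip visit 1, so the visit 1 text cannot describe any allocation for their later phases.

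**Conclusion.** The point holds as a contradiction with a consequence. The protocol gives two times for randomisation, and the one stated more often allocates men to a named product before laboratory and discretionary eligibility is settled and, in Phases II and III, 1-6 weeks before the first dose. That leaves the between-arm comparison open to selection after allocation.

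A reader might infer that the comparison is biased by a known amount. The documents do not support that: neither direction nor size can be derived. The illustrations run from no bias, through about a third to a half of a standard error, to more than one standard error in the harsher cases. All rest on assumed splits of the 20% by arm and timing, on assumed correlations or tail selection, and on the arm being known before visit 2. The change should be made because it closes an avoidable route to bias at almost no cost, not because a bias of a given size has been shown.

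**What to change.** - Abstract (Design, Phases I, II and III) and Lay Summary: delete randomisation from visit 1.
- Procedures, Visit 2: keep the randomisation sentence. Add that the assignment is released only after all screening results and the final eligibility ruling are recorded, immediately before product is dispensed. In Phase I, release it before the visit 2 procedures.
- Procedures, Visit 2, Phases II and III: replace the statement that the assignment is reviewed with one that the study group is assigned at that point.

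The investigational drug service, which already dispenses product, could hold the assignments and release each one. The cost is a handful of protocol sentences, with no added visit or procedure. The small downside is that both products must be in stock on every dispensing day, because the arm is not known beforehand.

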# **INCLUSION CRITERIA FOR MSM**

- 1) HIV-negative man who reports receptive anal sex with another man in the last 6 months
- 2) Male to female transgender women who have sex with men who report receptive anal intercourse with another man in the last 6 months and are not currently taking hormonal therapy or plan to take hormonal therapy for the duration of the study
- 3) Aged 18-49 years
- 4) Not currently taking PrEP and no plans to initiate during study
- 5) Able to provide informed consent in English
- 6) No plans for relocation in the next 3 months
- 7) Willing to undergo peripheral blood and rectal biopsy sampling
- 8) Willing to use study products as directed
- 9) Willing to abstain from receptive anal intercourse 3 days prior to starting study product and for the duration of the study and for 7 days after any rectal biopsy procedure.

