# Visit 1

# Phase I, II, and III

During the screening visit, eligible MSM will provide written informed consent after all their questions are answered in a private exam room at the Hope Clinic. Subjects will also receive an approved HIPAA statement and will be informed about the way their protected health information will be used and stored. Copies of the consent/HIPAA form for this project will not be placed in individuals' medical records since this study collects sensitive information such as HIV status and sexual orientation.

After provision of informed consent, a medical history and physical examination will be conducted by the PI to evaluate for exclusion criteria. A rapid HIV test with finger stick whole blood (Determine or other CLIA waved product) will be performed by the PI or study coordinator who will be certified in HIV counseling and testing to confirm eligibility. Peripheral blood will be drawn for a complete blood count, creatinine, and coagulation tests.

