# Phase III

40 participants (20 in each study arm) will be enrolled in study phase 2.

Study visit 2 will occur 1-6 weeks after the screening visit. During visit 2, the study group assignment will be reviewed and participants will be provided with a 10 day supply of Truvada® or Genvoya®. Drug will be dispensed through the Emory Investigational Drug Service. Depending on the study arm they were assigned to, MSM will be dispensed 10 days of Truvada® or Genvoya® and instructed on dosing for 10 consecutive days prior to their scheduled study visit 4. MSM will be requested to abstain from receptive anal intercourse while on study product. Participants will be scheduled to return for their third study visit after taking the study product for 3-5 consecutive days.

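### Participants who re-enter for a dosing phase can be given drug on a scheduled HIV test at least 63 days old; a rapid test before dispensing would close most of this gap

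*Protocol*

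**What the plan says.** **Re-entry (Protocol, Abstract).** A person may join more than one phase, provided "at least 8 weeks must lapse after completion of 1 study phase before entry into another". No upper limit on that gap is given. Those who re-enter "do not have to repeat the screening visit (visit 1) when starting another phase; they will begin the new phase at visit 2".

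**HIV testing (Protocol, Study visits, Visit 1).** The screening visit includes "A rapid HIV test with finger stick whole blood" to confirm eligibility. The descriptions of visits 2, 3 and 4 list no HIV test.

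**Dispensing (Protocol, Visit 2).** In phase II, "participants will be provided with a single dose of Truvada" or the comparator. In phase III, "participants will be provided with a 10 day supply of Truvada" or the comparator. On timing, the phase II text says "Study visit 2 will occur 1-6 weeks after the screening visit", and phase III has the same rule. Neither says how this applies to someone who re-enters.

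**Retest for cause (Protocol, risk section, paragraph on HIV drug resistance).** Men are tested at study entry and then asked at visits about risk behaviour and signs of acute infection. If either is reported, an HIV antibody test is repeated. The HIV risk counseling section says what happens if someone tests positive before visit 2 or 3, but schedules no test at those points.

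**Duration (Protocol, Abstract).** "Participants will be considered 'on-study' for no more than 12 weeks".

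**The concern.** A first entrant to phase II or III gets drug 1 to 6 weeks after a negative HIV test. A re-entrant may get it with no test since the one taken before the previous phase, with a gap of at least 8 weeks in between. The re-entry rule removes the visit that holds the test and puts nothing scheduled in its place.

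Infection during the gap is possible in this population. Eligibility requires reported receptive anal intercourse in the last 6 months, and criterion 4 reads "Not currently taking PrEP and no plans to initiate during study". The protocol also says why HIV status at dosing matters. In the PrEP trial it cites, resistance was found in 2 of 2 men on active drug who were acutely infected at enrolment, and in none of 100 men infected later. What is at stake is giving antiretrovirals to someone who was infected after visit 1 and whom nobody has a prompt to retest.

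**Working it through.** The documents give no figure for test age at re-entry, so there is none to reproduce. The check is calendar arithmetic on the protocol's own intervals.

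**Inputs**
- Screening to visit 2: 1-6 weeks, or 7 to 42 days (Visit 2, all phases).
- Visit 2 to the last visit of the phase: phase I, 0 days (visit 2 is the last visit); phase II, 1 day (visit 3 is 24 hours after dosing); phase III, 10 days (visit 4, taken as 10 days after visit 2).
- Gap before the next phase: at least 8 weeks, or 56 days (Abstract).

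**Formula.** Age of the visit 1 test at the new visit 2 = (screening to visit 2) + (visit 2 to completion) + (gap).

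| Phase already completed | Minimum age, days | If visit 2 was at week 6 and the gap is exactly 8 weeks, days |
|---|---|---|
| I | 7 + 0 + 56 = 63 | 42 + 0 + 56 = 98 |
| II | 7 + 1 + 56 = 64 | 42 + 1 + 56 = 99 |
| III | 7 + 10 + 56 = 73 | 42 + 10 + 56 = 108 |

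First entrants: 7 to 42 days. Even the shortest re-entry path (63 days) gives an older test than the longest first-entry path (42 days).

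**Third phase.** With I and II completed, the minimum before phase III dosing is 7 + 0 + 56 + 1 + 56 = 120 days. So 63 days is the lower bound over all sequences.

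**Effect of the 12-week limit.** Suppose the 84 days run from visit 1 and span phases. The new phase must then finish by day 84, so dosing is at latest day 84 − 1 = 83 on entering phase II and day 84 − 10 = 74 on entering phase III.
- I then II: 63 to 83 days.
- III then II: 73 to 83 days.
- I then III: 63 to 74 days.
- II then III: 64 to 74 days.

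On that reading the figures of 98 to 108 days, and any third phase, cannot occur. If the limit applies to each phase separately, they can, and a longer gap gives still older tests. The minimum values are the same on both readings.

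**Who is left uncovered.** The retest is triggered by reported risk behaviour or by reported symptoms; one is enough. A symptom-free man who reports a qualifying exposure is retested, and so is a man with symptoms who reports no exposure. Only a re-entrant who reports neither reaches dispensing on the old test alone.

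**The case against.** **The test-age comparison is not a breach of a limit.** A reader might take 63 − 42 = 21 days as the amount by which dosing overruns the protocol's own screening window. The documents do not support that. The 1-6 weeks schedules a visit; nothing says that an HIV test expires at 42 days. The re-entry rule is the more specific one and sends people straight to visit 2. What stands is that the test is older than any first entrant's, and that the visit 2 text does not say how its timing rule applies at re-entry.

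**The existing safeguard is wider than it may look.** A reader might infer that every symptom-free infection is missed. It is not, because reported exposure alone triggers a retest. Participants are also counselled and offered condoms. Inclusion criterion 9 asks for willingness to abstain from receptive anal intercourse for the duration of the study, although the operational instructions cover only the run-up to dosing in phase II, the dosing period and the week after biopsy. These points narrow the gap but do not close it.

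**A test may be listed elsewhere.** Figure 1 is not shown and could include one. The wording about a positive test before visit 2 or 3 hints at later testing, though the for-cause retest would also explain it. Likewise, the promise to test at study entry could be meant for each phase, but re-entrants are told to start at visit 2. The point therefore holds for the readable text only.

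**The benefit is modest.** The protocol calls resistance very rare except in men acutely infected at enrolment, and very recent infection is what a rapid test may miss. Exposure is one dose or 10 days. All of this is fair and keeps the point small. A retest would still find infection established during the gap, which nothing scheduled now does.

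**Conclusion.** The point holds as a cheap participant-safety improvement. In the readable text, someone entering phase II or III after another phase can be given drug on a scheduled HIV test at least 63, 64 or 73 days old (after phase I, II or III), against 7 to 42 days for first entrants.

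It rests on three assumptions: Figure 1 adds no test at visit 2; a phase is complete at its last clinic visit; and the re-entrant uses the option to skip visit 1. A later definition of completion would only raise the minimum values.

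The people affected are re-entrants who report neither risk behaviour nor symptoms. The documents give neither the number of re-entrants nor an infection rate, so no expected count of missed infections can be calculated, and the group may be empty. A reader might also infer a threat to the comparison of the two drugs. Nothing in the documents supports that: the re-entry testing rule is the same in both arms, and the SAP's drug-level analysis does not depend on it.

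**What to change.** In the Abstract, after the re-entry rule, add a sentence such as: *Anyone entering phase II or III without repeating visit 1 will have a rapid HIV test at, or shortly before, visit 2 of the new phase, and drug will be dispensed only if the result is negative.* A test on the day of visit 2 would bring its age at dispensing to 0 days.

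In the Visit 2 text for phases II and III, state that the 1-6 week window applies to first entry. If Figure 1 already lists such a test, the text need only be brought into line with it.

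The cost is one finger-stick test per re-entry, with the product already used at visit 1, and two short text edits. Sample size, endpoints and analysis do not change. Very recent infection may still be missed, so the existing questions about symptoms and risk behaviour should stay.
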